6.1.2 Sample size evaluation on key secondary endpoints

Return to work

Return to work is defined as the time in days patients need following a procedure to return to work. Return to work time can be influenced by factors that are independent of the type of work they are employed to do (e.g., including physical effort), the type of anesthesia that is used with or without hospitalization, and other regional/cultural differences.

To minimize the effects of independent factors that may influence the return-to-work time, several measures will be taken into account. Employment status will be captured for all patients. Only patients who have an active employment status (employed or independent worker, including stay at home parents) will be included in the analysis for return-to-work time. Information will be captured on the category of occupation to be able to distinguish between physical and sedentary work. A sensitivity analysis will be performed to investigate whether the day of the week of the procedure has an effect on the time to return to work. The sensitivity analysis will be a regression where the treatment arm and the day of the week of the procedure will be included as predictors.

A literature search on historical data for return-to-work time following treatment of venous reflux disease was conducted using the Pubmed database of clinical literature. Publications describing return to work times for treatment of venous reflux disease with the VenaSeal™ closure device, any type of endovenous laser ablation (EVLA) and radiofrequency ablation (RFA), or surgical stripping were considered. The resulting return to work times are summarized in Table 1, below. Where applicable, the return to normal activities time is included. The corresponding sample size (based on ITT) and measure of return time (mean vs. median) are included in the table. The results of the first five rows were used to estimate sample sizes for the return-to-work endpoint because these studies specifically report the mean and SD. Using a conservative approach, the resulting SDs for the three treatment groups (ETA, VenaSeal™ treatment, and surgical stripping) were compared against the median and IQR of the remaining findings to make sure the used estimation was justified compared to existing data. With this approach, the smallest differences between treatment with the VenaSeal™ device and the other treatments are utilized to calculate final sample size.

Table 1: Return to work/normal activity time post treatment of venous reflux disease (External Data)

Author	Treatment type	Sample size (# pts, ITT)	Measure	Time in days to return to normal activities	Time in days to return to work
Pronk	ETA: Laser	62	Mean (SD)	3.2 (4.3)	4.4 (5.4)
Lurie	ETA: RFA	45	Mean (95% CI)	1.15 (0.05-2.34)	4.7 (1.16-8.17)
Gibson	VenaSeal™	50	Mean (SD)	2.4 (+/- 4.1)	0.2 (+/- 1.1)
Lurie	Surgical stripping	40	Mean (95% CI)	3.89 (2.67-5.12)	12.4 (8.66-16.23)
Pronk	Surgical stripping	68	Mean (SD)	3.2 (4.0)	4.2 (3.7)
Samuel	ETA: Laser	38	Median (IQR)	4 (1-14)	4 (0-12)
	ETA: Laser	38	Median (IQR)	3 (1-14)	3 (1-8)
Rasmussen	ETA: Laser	125	Median (range)	2 (0-25)	3.6 (0-46)
Cotton	ETA: Laser	212	Median		7.7
Lattimer	ETA: Laser	56	Median (IQR)	7.5 (2-15)	

Carradice	ETA: Laser	140	Median (IQR)	3 (1-10)	4 (2-14)
Rasmussen	ETA: RFA	125	Median (range)	1 (0-30)	2.9 0-14
Lane	ETA: RFA	83	Median (IQR)	2 (1-7)	2 (2-7)
Subramonia	ETA: RFA	48	Median (IQR)	3 (2-5)	10 (4-13)
Chan	VenaSeal™	29	Median (range)		1 (1-16)
Subramonia	Surgical stripping	45	Median (IQR)	12.5 (4-21)	18.5 (11-28)
Carradice	Surgical stripping	140	Median (IQR)	14 (7-25)	14 (13-28)
Cotton	Surgical stripping	294	Median		11.7
Rasmussen	Surgical stripping	125	Median (range)	4 (0-30)	4.3 (0-42)

The null hypothesis for the key secondary endpoint is that the VenaSeal™ system arm will have the same days to return to work as that of the control (ETA or surgical stripping) arm. The alternative hypothesis is that the VenaSeal™ system arm will have different days to return to work than that of the control arm. Rejection of the null hypothesis in favor of VenaSeal will signify that the ability to return to work after treatment with the VenaSeal™ system is superior to ETA or surgical stripping.

Specifically, the null (H_0) and alternative (H_a) hypotheses are:

$$H_0: r_A = r_C$$

$$H_a: r_A \neq r_C$$

Where r_A and r_C are the true days of return to work for the VenaSeal™ system arm and ETA or surgical stripping arm, respectively.

The parameter assumptions are:

- $r_A = 0.2$ in the VenaSeal™ system arm and $r_C = 3$ and 8 in ETA arm and surgical stripping arm, respectively
- standard deviation of 1.1 in the VenaSeal™ system arm, 2 in ETA arm and 3 in surgical stripping arm
- Two-sided t test with $\alpha = 0.0167$
- 1:1 randomization

With these assumptions, a total of 22 subjects (evaluable; 11 in each arm) in the VenaSeal vs. ETA study and 10 subjects (evaluable; 5 in each arm) in VenaSeal vs. surgical stripping study will yield 90% power to reject the null hypothesis in favor of the alternative hypothesis of superiority in each study.

Closure rate

Closure rate is a generally used measure to determine the long-term success of venous reflux disease treatment. Literature may report on closure rate, occlusion rate, or recanalization rate at various moments in time. The endpoint used in this study focuses on the closure rate measured at 6 months.

To calculate the sample size based on historical data on closure rate, a literature search was conducted using the Pubmed database of clinical literature. Any literature older than 10 years was excluded from the analysis. Six-month closure rates for treatment of venous reflux disease with the VenaSeal™ closure device, any type of endovenous laser ablation and radiofrequency ablation, or surgical stripping were considered.

Closure rates were weighted within a treatment arm by multiplying the closure rate for that treatment with the sample size of the treatment arm. Table 2 below shows an overview of the literature that was used to calculate weighted closure rates that were used for sample size calculations.

Table 2: Closure Rates for Treatment of Venous Reflux Disease

Author	Year	Treatment	Follow-up	Sample size (# pts, ITT)	Closure/occlusion rate
Brittenden	2015	ETA: Laser	6M	212	83.0%
Bozoglan	2016	ETA: Laser	6M	60	100.0%
Eroglu	2018	ETA: Laser	6M	175	95.1%
Sydnor	2017	ETA: Laser	6M	100	100%
Wozniak	2016	ETA: Laser	6M	56	100%
Mese	XXXX	ETA: Laser	6M	60	100%
Atasoy	2015	ETA: Laser	6M	44	100%
Calik	2019	ETA: Laser	6M	200	95.6%
Lane	2016	ETA: RFA	6M	82	93.0%
Beteli	2017	ETA: RFA	6M	43	95.3%
Eroglu	2018	ETA: RFA	6M	175	94.1%
Sydnor	2017	ETA: RFA	6M	100	97.3%
Mendes	2016	ETA: RFA	6M	18	80.0%
Wozniak	2016	ETA: RFA	6M	54	100%
Mese	2015	ETA: RFA	6M	60	95.0%
Yang	2013	ETA: RFA	6M	100	99.0%
Morrison	2018	ETA: RFA	6M	114	96.2%
Creton	2010	ETA: RFA	6M	295	98.6%
Chan	2017	VenaSeal™	6M	57	90.3%
Almeida- FIH	2013	VenaSeal™	6M	38	92.1%
Gibson - WAVES	2016	Venaseal™	6M	70	98.0%
Proebstle- eSCOPE	2015	VenaSeal™	6M	70	91.4%
Morrison- VeClose	2018	VenaSeal™	6M	108	99.0%
Brittenden	2015	Surgical stripping	6M	294	84.4%
Jia	2010	Surgical stripping	6M	26	89.5%

Table 3 shows an overview of the weighted average closure rates at 6 months that were used to calculate the sample size for this endpoint.

Table 3: Weighted Average Closure Rate

Comparator	Total number of considered studies	Total sample size in considered studies	Weighted average closure rate at 6M
VenaSeal™	5	343	95.0%
ETA	18	1948	95.4%
Surgical stripping	2	320	84.8%

The null hypothesis on this key secondary endpoint is that the closure rate at 6 months in the VenaSeal™ system arm will have less than or equal to that in the control (ETA or surgical stripping) arm minus a clinically relevant difference of 10%. The alternative hypothesis is that the closure rate at 6 months in the VenaSeal™ system arm will be greater than that in the control arm minus a clinically relevant difference of 10%. Rejection of the null hypothesis will signify that the treatment with the VenaSeal™ system is not inferior to the treatment with ETA or surgical stripping.

Specifically, the null (H_0) and alternative (H_a) hypotheses are:

$$H_0: \pi_A \leq \pi_C - 10\%$$

$$H_a: \pi_A > \pi_C - 10\%$$

Where π_A and π_C are the closure rate at 6 months in the VenaSeal™ system arm and the ETA or surgical stripping arm.

The parameter assumptions are:

- $\pi_A = 95\%$ in the VenaSeal™ system arm and $\pi_C = 95.4\%$ and 84.8% in ETA and surgical stripping arm, respectively
- Likelihood Score (Farrington & Manning) test with one sided $\alpha = 0.0167$
- 1:1 randomization
- 10% attrition rate

With these assumptions, a total of 264 subjects (238 evaluable, 119 in each arm) will yield 80% power to reject the null hypothesis in favor of the alternative hypothesis of non-inferiority to the ETA arm. A total of 98 subjects (88 evaluable, 44 in each arm) will yield 80% power to reject the null hypothesis in favor of the alternative hypothesis of non-inferiority to the surgical stripping arm.

6.1.3 Overall Sample Size Evaluation

Power Analysis and Sample Size (PASS) was used to compute sample size. Based on the above fixed sample size calculations, the total sample size in the VenaSeal vs ETA study will be 264, to demonstrate the success on each primary endpoint with at least 90% power, as summarized in Table 4 below.

Table 4: Primary or Key Secondary Endpoint Sample Size for Randomized Studies

Primary or Key Secondary Endpoint	Total Sample Size: VenaSeal and ETA Arms	Total Sample Size: VenaSeal and Surgical Stripping Arms
VenousTSQe at 30 days	237	237
VenousTSQs at 30 days	237	237

Elimination of truncal reflux at index procedure	227	220
Return to work	22	10
Closure rate at 6 months	264	98
Overall Sample Size (Including Attrition)	264	237

The total sample size in the VenaSeal vs Surgical Stripping Study will be 108 subjects due to the enrollment closure on 22-Feb-2022.

6.1.4 Sample Size Re-estimation

No interim analysis sample size re-estimation is planned for the VenaSeal vs. ETA Study or the VenaSeal vs. Surgical Stripping Study.

6.2 VLU Study (Single-Arm Study)

6.2.1 Sample Size Consideration

The primary endpoint in the VLU Study is time to ulcer healing. For reference, the EVRA study evaluated clinical and cost effectiveness of early endovenous treatment and standard care vs. deferred intervention in patients with chronic venous ulceration. As there are no statistically powered hypotheses in the VLU Study, precision estimates (distance from point estimate to upper 95% two-sided confidence bound) were used to derive the sample size based on the outcomes of the EVRA study.

In comparison to the EVRA study, criteria for VLU Study inclusion are less restrictive, which may result in an ulcer population which is older and heals more slowly than the EVRA early-intervention group. Precision calculations utilized an assumed median time to healing of 70 days which is the approximate average of the median healing time between the EVRA early-intervention and deferred-intervention groups (56 and 82 days, respectively). Precision estimates for a range of sample sizes are provided in Table 5. A simulation was run 10,000 times on the assumption of exponential distribution of 70 days median time to healing. The simulation results show that a precision of less than 23 days can be obtained with a sample size of 125 subjects enrolled in the VLU Study.

Table 5: Sample Size for the VLU Study

Sample size	Evaluable Sample Size (10% attrition)	Precision
80	72	<30 days
90	81	<28 days
100	90	<26 days
110	99	<25 days
115	104	<24 days
120	108	<24 days
125	113	<23 days

7. Statistical Methods

7.1 Study Subjects

7.1.1 Disposition of Subjects

The number and percentage of subjects screened, enrolled, received therapy and completed each scheduled clinical follow-up visit will be summarized. The number and percentage of subjects who complete the study and who exit early will be summarized by exit reason as documented on the case report form (CRF). The subject clinical follow-up compliance will be provided at each study visit by study arm via a flow diagram and/or table.

The VenaSeal vs. Surgical Stripping Study was originally planned to have 5 years of subject follow-up. However, in CIP version 4.0, the follow-up was reduced to 12 months and the endpoints were updated accordingly. It is likely that some subjects will collect data beyond 12 months during transition of the CIP change. Data collected beyond 12 months will be reported in listings. If there is a sufficient sample size for some endpoints, these endpoints may also be summarized.

7.1.2 Clinical Investigation Plan (CIP) Deviations

A deviation is any event in which the study is not conducted according to the CIP, applicable laws or regulations or the Investigator Agreement.

Protocol deviations will be reported descriptively by counts of type and be listed by identifying site. Counts of deviations, number and percentage of subjects who have CIP deviations will be summarized by associated visit and reason as documented in the CRF. Results will be summarized by study arm for the randomized studies.

7.1.3 Analysis Sets

CEAP 2-5 randomized studies

The primary analysis set for Randomized Studies will be the ITT analysis set. Per-protocol (PP) analyses may be performed as a sensitivity analysis. All analysis sets have been defined with the intent of minimizing bias in the data analysis.

Intent-to-Treat (ITT): All patients who are randomized in the arms in each study will be included in the analysis regardless of the treatment received or the outcome of the treatment.

Per-Protocol (PP): The ITT population excluding failed and no procedure treatment outcomes, subjects that are treated with the modality they were not randomized to and/or have not met the inclusion/exclusion criteria. A failed procedure with no procedure treatment outcomes is defined as a procedure where the procedure treatment was never attempted or a procedure that was aborted.

As treated (AT): Includes subjects in the arm they are treated with according to the treatment actually received, regardless of the arm they were randomized to.

VLU (single arm) Study

Intention-to-Treat (ITT): All patients with CEAP 6 who are enrolled in this study (either successful, incomplete or failed treatment outcome) will be counted in the ITT population, which will be the primary analysis set.

Per-Protocol (PP): The ITT population excluding failed treatment outcome and/or subjects that have not met the inclusion/exclusion criteria. A failed procedure with no procedure treatment outcomes is defined as a procedure where the procedure treatment was never attempted or a procedure that was aborted.

The primary analysis for this CEAP 6 single arm study will be on intention-to-treat (ITT) population. All analysis sets have been defined with the intent of minimizing bias in the data analysis.

7.2 General Methodology

Descriptive statistics of continuous characteristics/outcomes will be presented and include sample size, mean, median, standard deviation, minimum, and maximum. For categorical outcomes, the count and percentage of subjects in each category will be presented. Subject data listings and tabular and graphical presentations of results will be provided. All analyses will be based on ITT principle, unless otherwise specified. All statistical analyses will be performed using Statistical Analysis System (SAS) software (version 9.4 or higher) or other widely accepted statistical or graphical software.

7.3 Center Pooling

For each study, data will be pooled across sites for analysis. Results will be also summarized and presented for primary and key secondary endpoints by site for each study.

7.4 Handling of Missing, Unused, and Spurious Data and Dropouts

Every effort will be undertaken to minimize missing data. A combination of sensitivity analysis and multiple imputation of the primary endpoints will be performed to assess the potential impact of missing data. The details will be described in the section 7.9.1.1.6 Missing Data Analysis below.

Unless otherwise specified, no statistical techniques will be used to impute missing data for the other objectives. The number of subjects included in each analysis will be reported. In time-to-event outcomes drop-outs will be censored at the time of discontinuation, consistent with the Kaplan-Meier approach.

7.5 Adjustments for Multiple Comparisons

In the randomized studies, Hochberg procedure will be used in the adjustments for multiple comparisons on primary and key secondary endpoints (Benjamini & Hochberg, 1995)¹. Familywise type I error 0.05 will be used for the primary endpoints and type I error preserved from the primary endpoints will be used for the key secondary endpoints.

VenaSeal vs. ETA Randomized Study

In each randomized study, p-values for the primary endpoints will be ordered from largest to smallest as $p_{p1} > p_{p2} > p_{p3}$ from the 3 hypothesis tests H_{p1}, H_{p2} and H_{p3} , and for the key secondary objectives in descending order as $p_{s1} > p_{s2}$ from the 2 hypothesis tests for key secondary endpoints H_{s1} and H_{s2} , the procedure is as follows:

Step 1. If $p_{p1} < \alpha$, then claim success on all 3 hypotheses for primary endpoints H_{p1}, H_{p2} and H_{p3} ; and proceed to Step 1a, otherwise, go to step 2.	
Step 1a. If $p_{s1} < \alpha$, then claim success on both hypotheses for key secondary endpoints H_{s1} and H_{s2}; otherwise, go to step 1b.
 
Step 1b. If $p_{s2} < \alpha/2$, then claim success on hypothesis for key secondary endpoint H_{s2}; otherwise, both hypotheses for key secondary endpoints H_{s1} and H_{s2} are unsuccessful

Step 2. If $p_{p2} < \alpha/2$, then claim success on two hypotheses for primary endpoints H_{p2} and H_{p3} ; and proceed to Step 2a, otherwise, go to step 3.	
Step 2a. If $p_{s1} < \alpha/2$, then claim success on both hypotheses for key secondary endpoints H_{s1} and H_{s2}; otherwise, go to step 2b.
 
Step 2b. If $p_{s2} < \alpha/4$, then claim success on hypothesis for key secondary endpoint H_{s2}; otherwise, both hypotheses for key secondary endpoints H_{s1} and H_{s2} are unsuccessful

Step 3. If $p_{p3} < \alpha/3$, then claim success on hypothesis for primary endpoint H_{p3} ; and proceed to Step 3a, otherwise, no success on all 3 hypotheses for primary endpoints H_{p1}, H_{p2} and H_{p3}	
Step 3a. If $p_{s1} < \alpha/3$, then claim success on both hypotheses for key secondary endpoints H_{s1} and H_{s2}; otherwise, go to step 3b.
 
Step 3b. If $p_{s2} < \alpha/6$, then claim success on hypothesis for key secondary endpoint H_{s2}; otherwise, both hypotheses for key secondary endpoints H_{s1} and H_{s2} are unsuccessful

$\alpha = 0.05$ for Endothermal Ablation (ETA) study.	

VenaSeal vs. Surgical Stripping Randomized Study

In each randomized study, p-values for the primary endpoints will be ordered from largest to smallest as $p_{p1} > p_{p2}$ from the 2 hypothesis tests H_{p1} , and H_{p2} , and for the key secondary objectives in descending order as $p_{s1} > p_{s2}$ from the 2 hypothesis tests for key secondary endpoints H_{s1} and H_{s2} , the procedure is as follows:

Step 1. If $p_{p1} < \alpha$, then claim success on both hypotheses for primary endpoints H_{p1} , and H_{p2} ; and proceed to Step 1a, otherwise, go to step 2.	
Step 1a. If $p_{s1} < \alpha$, then claim success on both hypotheses for key secondary endpoints H_{s1} and H_{s2}; otherwise, go to step 1b.
 
Step 1b. If $p_{s2} < \alpha/2$, then claim success on hypothesis for key secondary endpoint H_{s2}; otherwise, both hypotheses for key secondary endpoints H_{s1} and H_{s2} are unsuccessful

Step 2. If $p_{p2} < \alpha/2$, then claim success on endpoint H_{p2} , otherwise, no success	
Step 2a. If $p_{s1} < \alpha/2$, then claim success on both hypotheses for key secondary endpoints H_{s1} and H_{s2}; otherwise, go to step 2b.

on both hypotheses for primary endpoints H_{p1} , and H_{p2}	Step 2b. If $p_{s2} < \alpha/4$, then claim success on hypothesis for key secondary endpoint H_{s2} ; otherwise, both hypotheses for key secondary endpoints H_{s1} and H_{s2} are unsuccessful
$\alpha = 0.05$ for VenaSeal vs. Surgical Stripping Randomized Study.	

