6.1 Randomized Studies

Analyses will be performed on all patients who pass the point of enrollment (randomization), as according to the intention-to-treat (ITT) principle. Patients will be analyzed in the arm they are randomized to regardless of the treatment received.

There are three primary endpoints and two key secondary endpoints with formal hypothesis testing for the Randomized Studies. Multiplicity adjustment needs to be considered to control the overall type I error. Each randomized study will have a family-wise type I error rate of 0.05. Within each study, Hochberg procedure will be used to control the family-wise type I error rate to 0.05 for the primary endpoints (Benjamini & Hochberg, 1995)¹. Type I error preserved from the primary endpoints will be used for the key secondary endpoints.

A type I error of 0.0167 will be used in the following sample size calculations for this purpose.

In the two Randomized Studies, three primary endpoints will be assessed:

- 1) Peri-procedural patient satisfaction as measured by a validated patient-centered venous treatment satisfaction questionnaire (VenousTSQe) at 30 days;
- 2) Patient satisfaction as measured by a validated patient-centered venous treatment satisfaction questionnaire (VenousTSQs) at 30 days, and
- 3) elimination of clinically relevant superficial truncal disease in each target vein at index procedure. The two key secondary endpoints include achieving the anatomical closure of primary target superficial truncal veins at 6 months and the time to return to work post-index procedure.

For VenaSeal vs Surgical Stripping Study, 108 subjects randomized before 22-Feb- 2022 will be included in the analysis. These subjects will be followed for 12 months after index procedure. Since the enrollment was stopped for the VenaSeal vs. Surgical Stripping Study with up to 108 subjects, there is still reasonable power for the two TSQs and key secondary objectives. Therefore, the VenaSeal vs. Surgical Stripping Study will test two primary endpoints (Venous TSQe and TSQs at 30 days) and the key secondary endpoints. The elimination of truncal reflux at the index procedure will be summarized but not tested for hypothesis testing.

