7.9 Evaluation of Objectives

VenaSeal vs. Surgical Stripping

2 primary endpoints and 2 key secondary endpoints will be evaluated.

VenaSeal vs. ETA

3 primary endpoints and 2 key secondary endpoints will be evaluated.

VLU Single Arm Study

No hypothesis testing will be done.

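### SAP 7.5 passes alpha/2 or alpha/3 to the key secondaries after a partial Hochberg win, so study-wise error can reach about 7.4% against the stated 5%

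*SAP*

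**What the plan says.** **The error rate promised.** SAP 6.1 states: "Each randomized study will have a family-wise type I error rate of 0.05". Protocol 14.1 carries the same sentence. In both documents it follows directly on the list of hypotheses to be controlled: "There are three primary endpoints and two key secondary endpoints with formal hypothesis testing for the Randomized Studies". For the stripping study, SAP 7.9 reduces the list: "2 primary endpoints and 2 key secondary endpoints will be evaluated".

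**The allocation rule.** SAP 7.5 commits the full 0.05 to the primaries and then states: "type I error preserved from the primary endpoints will be used for the key secondary endpoints".

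**The steps (SAP 7.5, alpha = 0.05).** The largest primary p-value is compared with the full alpha: "Step 1. If $p_{p1} < \alpha$, then claim success on all 3 hypotheses for primary endpoints". If that fails, the second largest is compared with alpha/2 and, on success, the instruction is "and proceed to Step 2a, otherwise, go to step 3". The key secondaries are then tested by Hochberg at the reduced level: "Step 2a. If $p_{s1} < \alpha/2$, then claim success on both hypotheses for key secondary endpoints".

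| Study | Primaries won | Level passed to key secondaries |
|---|---|---|
| ETA | 3 of 3 | alpha |
| ETA | 2 of 3 | alpha/2 |
| ETA | 1 of 3 | alpha/3 |
| Stripping | 2 of 2 | alpha |
| Stripping | 1 of 2 | alpha/2 |

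Neither document describes a truncation fraction or any alpha held back from the primaries.

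**The concern.** Hochberg is more powerful than Bonferroni because it tests the last remaining primary at the full alpha. If two primaries have clear effects and the third has none, the null primary is in effect tested at 0.05, and that uses the entire study budget. When it fails, no error is preserved. The SAP nonetheless opens a second family at 0.025 (or 0.0167), and that error adds to the 0.05 already spent. Alpha is legitimately released only in Step 1, when every tested primary is rejected.

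The claims at stake are superiority on return to work and non-inferiority on 6-month closure after a partial primary win. Those claims would be presented as controlled at 5% study-wise when they are not.

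**Working it through.** **Inputs.** Alpha = 0.05 per study (SAP 6.1, Protocol 14.1). Step levels as tabulated above (SAP 7.5). Planning effect of 0.5 SD with 110 evaluable per arm, and 7% attrition (SAP 6.1.1). The correlation between endpoints is not given; it is assumed to be 0 for the headline figure, with a range shown.

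**1. The plan's own figure, primaries only.** Ordinary Hochberg on two independent true nulls at level L rejects at least one with probability L² + 2(L/2)(1 − L) = L. At L = 0.05 this is 0.05. Simulating the primary steps alone also gives 0.05 or less. The stated 0.05 therefore holds within the primary family.

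**2. Key secondaries at the passed level.** The same identity with L = alpha/2 gives 0.025, and with L = alpha/3 it gives 0.0167, when both key secondaries are null. If one key secondary is real and the other null, the null one is tested at L itself, so the error is again L.

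**3. Whole procedure, independent tests, effective primaries certain to be rejected.**

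- ETA, 2 of 3 primaries effective: 0.05 + 0.95 × 0.025 = 0.0737. The additive bound, valid without independence, is 0.05 + 0.025 = 0.075.
- ETA, 1 of 3 effective: the two null primaries give 0.05 by step 1, so 0.05 + 0.95 × 0.0167 = 0.0658.
- Stripping, 1 of 2 effective: 0.05 + 0.95 × 0.025 = 0.0737.
- All primaries effective, or none: 0.05 or less, so no inflation.

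**4. Simulation of the written steps** (key secondaries null, common correlation between test statistics):

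| Scenario | Corr. 0 | 0.3 | 0.5 |
|---|---|---|---|
| ETA, 2 of 3 effective, certain wins | 7.4% | 7.2% | 6.9% |
| ETA, 1 of 3 effective, certain win | 6.6% | 6.4% | 6.0% |
| ETA, 2 of 3 effective at planned effect | 7.1% | 6.7% | 6.1% |
| Stripping, 1 of 2 effective, certain win | 7.4% | 7.2% | 6.8% |
| Alpha passed only after Step 1, ETA 2 of 3 or stripping 1 of 2 | 5.0% | 5.0% | 5.0% |

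The planned effect corresponds to a mean z of 0.5 × √(110/2) = 3.71. At correlations of 0.7 and 0.9, the first row falls to 6.3% and 5.5%.

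**5. Stripping study at its actual size.** 108 × 0.93 = 100.4, or about 50 per arm. With an SD of 1 per item the mean z is 0.5 × √(50/2) = 2.5, and power at alpha/2 is about 60%; the error is then 5.7%, 5.8% and 5.4% at correlations 0, 0.3 and 0.5. With the SAP's less conservative SD of 0.75 per item the mean z is 2.5/0.75 = 3.33, and the error is about 6.1% to 6.9%.

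**The case against.** Five points can be made for the plan.

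- **7.4% is a ceiling.** It needs independence, near-certain wins on the other primaries and exactly one null primary. That is right. Step 5 above shows that the stripping study is likely to sit lower, because its one effective primary would often be missed.
- **At least one key secondary must be truly null.** The design assumes large return-to-work differences and near-equal or better closure. If both key secondary effects are real, the error is 5.0%. This also stands, but a single null secondary restores about 7.4%, and an error guarantee cannot assume that the hypotheses under test are false.
- **Superiority is claimed only in VenaSeal's favour.** Counting only false claims in that direction, the ETA ceiling case gives about 4.3%. However, correct gating gives about 2.5% on the same measure, so the excess does not go away, and the documents state their 0.05 for two-sided primary tests.
- **The 0.05 may be meant for the primaries only.** SAP 7.5, and one sentence in SAP 6.1, tie it to them. But both documents also state it for each randomised study, and error preserved from one family for another has no meaning unless control spans both. If the narrow reading is intended, the wording still needs correcting.
- **Primary conclusions are unaffected.** True; the defect touches only key secondary claims made after a partial primary win.

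These points limit the typical size. They do not restore the stated property, because family-wise control has to hold under every configuration of true and false nulls.

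**Conclusion.** The concern holds. The steps in SAP 7.5 do not control study-wise type I error at 0.05. The worst case is about 7.4% under independence (additive bound 7.5%), reached by the alpha/2 route in either study; the alpha/3 route gives about 6.6%. At planned power the two-of-three ETA case gives about 6.1% to 7.1% for correlations of 0.5 down to 0. The stripping study at its actual size gives about 5.4% to 6.9%, depending on the SD and correlation assumed. There is no inflation when all primaries or none are effective, or when both key secondary effects are real. The correlations are assumptions; the mechanism does not depend on them. A confirmatory plan should not state an error rate that its own decision rule exceeds, so this must be corrected.

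**What to change.** Choose one of the following before comparative results are known.

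**(a) Gate on all primaries.** Keep Step 1 with Steps 1a/1b. Delete Steps 2a/2b and 3a/3b for the ETA study and Steps 2a/2b for the stripping study. Simulated error returns to 5.0%. The cost is that no formal key secondary claim is possible after a partial primary win. This option only removes claims that the present steps would allow; it never adds one.

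**(b) Reserve alpha explicitly.** Use a truncated Hochberg with a fixed fraction γ below 1, or a Bonferroni/Holm-based graphical procedure. As an illustration with three primaries and γ = 0.5, the largest primary p-value is tested at 0.05 × (0.5 + 0.5/3) = 0.0333 instead of 0.05. After two wins of three, 0.05 − 0.0333 = 0.0167 passes on, and the independent-case error is 0.0333 + 0.9667 × 0.0167 = 0.0494. The cost is a little primary power.

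**(c) If neither is adopted,** amend SAP 6.1 and 7.5 and Protocol 14.1 to say that 0.05 is controlled within the primary family only, that study-wise error can reach about 7.4%, and that key secondary claims after a partial win carry this caveat.

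Options (a) and (b) need only SAP wording and code, with no change to data collection.
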